This is an ideal study setting. The intervention strategy we propose is based on our extensive experience conducting large-scale HIV prevention trials in Tanzania for over 17 years in collaboration with Muhimbili University. Over the past 8 years we have collected extensive data on HIV risk and

household characteristics from NIMH Project Accept – a multi-site community randomized Phase III trial assessing the efficacy of community-based HIV voluntary counseling and testing. We have mapped and enumerated all households in the district, done qualitative research, characterized HIV risk factors (behavioral and biologic), done cost-analyses, worked successfully with the local communities and health system, established a collaboration with the PEPFAR-funded AIDS treatment centers, and established a rural research infrastructure with experienced intervention and research staff. Our specific AIMS evaluate 4 key strategic goals, including:

1. HIV Self-Testing for Stable Couples: (a) assess the acceptability, safety, and factors associated with uptake of HIV self-testing; and (b) determine the proportion of clients testing positive for HIV via self-testing who engage in care.
2. Dyadic Engagement of Serodiscordant Couples in Care & Prevention: (a) establish the proportion of serodiscordant couples who will enroll in HIV care as a dyad, (b) determine the effect of dyadic care enrollment on retention and adherence, and (c) assess reduction in risk of acquiring HIV infection for the negative partner.
3. Pre-Exposure Prophylaxis (PrEP): (a) establish the proportion and characteristics of HIV negative clients in a serodiscordant relationship who opt to take PrEP, (b) determine how engaging in ARV treatment by the positive partner affects PrEP utilization by the negative partner, and vice versa, and (c) Identify patterns and correlates of risk reduction strategies that couples in care utilize over time (abstinence, ARV for positive partner, PrEP for negative partner, condom use).
4. Operational: (a) determine Dyadic-based Diagnosis, Care, & Prevention (DDCP) program cost and economic efficiency, (b) compare DDCP to clinic-based and mobile VCT with regard to cost and efficiency for testing and linkage to care, and (c) assess the feasibility, acceptability, safety, and utility of using biometric data to track service utilization.

B. BACKGROUND AND SIGNIFICANCE

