- Distribution of 2 HIV Self-test kits provided with instructions to go to study center if either partner tests HIV positive.
- Those presenting at study center will have confirmatory rapid HIV test (blood) and if infected referred and escorted to adjacent collaborating government HIV Care and Treatment Center (CTC).
- For the estimated 60 sero-discordant couples presenting, immediate access to ARV for positive partner, and access to PrEP for negative partner.
- Biometric data collected at each clinical visit for 60 sero-discordant couples, & 6-, 12-, & 18- month survey.
- Follow up interview with couples sampled at baseline and confirmatory rapid (blood) HIV test
- Clinical data on retention, adherence, client characteristics on existing patient population enrolled in HIV care at CTC collected for comparison.
- Detailed costing of all intervention components.

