Preparedness - Prior to initiating the study we will establish a Community Advisory Board (CAB). The CAB will have representatives from the community, and will include village leaders, representatives from civic groups, Mosques, health care providers, and other interested parties. We will convene meetings of the CAB every 6-months to seek advice, provide information, and solicit feedback on the safety and acceptability of the intervention. In our previous work the CABs have been invaluable to our study operations and in generating partnerships with communities.

Why Is There No Control Group?

- This is an exploratory study primarily investigating operational research issues: safety, acceptability, retention, adherence, uptake of intervention components, and cost. Randomization to a control condition would not significantly enhance the knowledge gained from the study for these questions.
- Measuring differences in HIV incidence across arms would be desirable. However, to measure HIV incidence would require that we test participants for HIV at baseline. It is unethical to withhold the HIV test results, and providing HIV testing at baseline would contaminate the control group, as they would receive a key element of the experimental intervention.
- For research questions requiring comparative data (e.g. retention in care, adherence to treatment) we will have access to blinded clinical data from the Care and Treatment Center for clients not enrolled in the study for comparison.
- For costing, economic efficiency, safety and acceptability we have excellent and recently collected data from the same geographic area from Project Accept for comparisons.

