Sampling of Households –Based on data from the 2012 census, Kisarawe Ward will be divided into sections by village and sub-village. To begin sampling, one village/sub-village will be selected. Once selected, data collectors will visit every household in the selected area. Once an entire section has been covered, data collectors will select a new section of the ward to sample. This process will continue until approximately 442 couples have been enrolled, although we may need to enroll up to 1000 couples as described earlier. To recruit for the second component of the study we will approach couples who participated in self-testing and are found to be serodiscordant. We will also recruit the serodiscordant cohort from patients already enrolled in care at the Kisarawe CTC. We will continue recruiting using both methods until 60 serodiscordant couples (but up to 70 as described earlier) have enrolled in the second part of the study. We may recruit more than 442 couples—but no more than 1,000 couples—in the self-testing component of the study in order to enroll 60 serodiscordant couples in the second part of the study. As well, we may enroll up to 70 serodiscordant couples in the second part of the study if we are continuing to finish out a geographic cluster with provision of HIV self-testing.

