
Clinical Data from Care and Treatment Center – Tanzania, with support from the Clinton Foundation, has implemented a medical records data information system in Care and Treatment Centers called the CTC2. This system records data on patient characteristics, enrollment, pharmacy data, retention, adherence, complications, and CD4 count (and we will add viral load to assess viral suppression at the 18-month follow-up study visit). We will have access to these data, and will, with participant consent, link biometric data for study participants to their clinical data. In addition, the CTC in Kisarawe will provide blinded CTC2 data on other clinic patients enrolled in the program to allow for comparison of client characteristics, retention, adherence, and viral suppression.

Quality Assurance & Quality Control – We will employ a number of strategies to minimize bias and maintain quality during data collection procedures. Field supervisors will revisit a sample of households that interviewers were assigned to visit and for which they reported the structure as non-residential or as a non-existent household, to verify the household status. In order to minimize selection bias in our sample, interviewers will visit an assigned household a minimum of three times, on different days and at different times, in order to establish contact with either the head of household (or other responsible adult), or the selected individual for study participation. Each interviewer will review each form for errors before leaving. Field supervisors will monitor interviewer progress with households and review data from every interview.

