6. Discontinue in-person study visits – (a) No hospital-based study activities – CTC2 card data extraction will pause beginning 1st May 2020. Additionally, no Data Collector will be stationed at the CTC for Monthly Clinical ART visits. (b) Only clinical PrEP visits will be conducted in-person – per guidance issued by MUSC IRB, NIMR, and MUHAS DRP, study visits should only continue if the withholding of medication would impose a greater risk to participants than potential exposure to COVID-19. Therefore, we will continue to provide PrEP medication to our HIV-negative participants. At the time of the first confirmed case in Tanzania, there were 13 seronegative participants who were still enrolled in the study and may come to the Study Center for PrEP through early August 2020. (c) Remainder of study surveys will be conducted over the phone – we already have IRB approval to conduct surveys over the phone with the participant's permission. The Nurse Supervisor, PrEP Nurse, and Interviewer Supervisor will attempt to call participants and record survey answers in the tablets. We will provide compensation money electronically via mobile money transfer (Halo-pesa). (d) No qualitative interviews – in-person qualitative exit interviews will pause beginning 1st May 2020.
7. Reduce staff load – In an effort to minimize exposure to staff and maintain social distance, only four technical staff (Study Coordinator, Nurse Supervisor, PrEP Nurse, Interviewer Supervisor), one driver, one cleaner, and one security guard will be on duty per week. The remaining field staff, drivers, cleaners, and security guards will be rotated out on a weekly basis.
8. Continued monitoring – The Principal Investigators, Co-Investigators, and Study Coordinators will continue to monitor the COVID-19 situation in Tanzania. The Tanzania-based team will provide regular updates to the South Carolina-based team to monitor the progress of the outbreak and community transmission within Tanzania and in Kisarawe District, specifically. We will update our procedures as necessary, maintaining the safety of staff and participants as the highest priority.

Analysis Plan

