
Evaluation of Specific Aims & Associated Hypotheses

AIM 1 - We hypothesize that the majority of couples (GT ~ 50%) will utilize the HIV self-test kits and share their results with their partner. To evaluate the factors associated with uptake of HIV self-testing, a single level logistic regression model with a logit link function will be performed. The outcome will be the HIV self-testing status (0 = did not use self-test, 1 = used self-test). Demographic variables (e.g., age & gender) will be evaluated as predictors of self-testing uptake, with results focusing on ORs, and corresponding 95% CIs.

AIM 2 - We hypothesize that a large proportion of serodiscordant couples who present to the study referral office (GT ~ 70%) will engage in care together, have higher rates of adherence and retention than individually enrolled clients, and have a reduction in risk behaviors for HIV transmission from baseline to 18-month follow up. For this aim, there are repeated measurements of retention in care and adherence (level-1) nested within positive partners (level-2). A dichotomous predictor variable at the individual level (i.e., level-2) will test for differences in the log-odds of treatment retention between those enrolled in care as a couple and those enrolled in routine clinic services. The adherence outcome will be analyzed in a similar manner. For this outcome, there are several indicators of medication adherence. First, for the positive member of the couples, self-reports of ARV adherence will be obtained at 6, 12, and 18 months. Second, individuals on ARV are expected to return to the clinic each month to have the prescription refilled. Third, for individuals in the study, viral load tests will be obtained at 18 months allowing us to assess viral suppression as a marker for medication adherence. For the

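### Aim 2(b) compares couple care with other clinic patients through one group indicator, with no common start month, comparator restriction or pre-specified covariates, so the coefficient mixes any dyadic effect with selection and time in care

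*Combined protocol and SAP*

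**What the plan says.** All references are to the combined protocol and SAP. The Specific Aims state Aim 2(b) as to "determine the effect of dyadic care enrollment on retention and adherence", and the AIM 2 analysis text adds the directional hypothesis that couples will do better than individually enrolled clients.

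For retention, AIM 2 says: "A dichotomous predictor variable at the individual level (i.e., level-2) will test for differences in the log-odds of treatment retention". The same couple-versus-routine indicator is used for 18 monthly refill values per person. CD4 at 18 months is compared between groups in a single-level regression, without mention of baseline CD4.

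The comparators are described in three places:
- The work summary (How will we do the work?): "Clinical data on retention, adherence, client characteristics on existing patient population enrolled in HIV care at CTC collected for comparison".
- Why Is There No Control Group?: "we will have access to blinded clinical data from the Care and Treatment Center for clients not enrolled in the study for comparison".
- Clinical Data from Care and Treatment Center: "blinded CTC2 data on other clinic patients enrolled in the program to allow for comparison of client characteristics, retention, adherence, and viral suppression".

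The study group has two sources. Some couples are found by self-testing, and the Sampling of Households text adds: "We will also recruit the serodiscordant cohort from patients already enrolled in care at the Kisarawe CTC".

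Under Model Building & Estimation, the Analysis Plan names a general approach to choosing fixed and random effects. AIM 2 allows other refill specifications after the plots have been inspected. Neither names a covariate for this comparison, although age and gender are named as predictors for Aims 1 and 3.

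**The concern.** The two groups differ by design in ways likely to affect retention. The eligibility text requires study couples to cohabit, to have no plans to move and to accept disclosure, with similar criteria for clinic recruits. Sources of Materials requires enough tracing information for follow-up. Human Subjects Involvement requires clinic-recruited couples to live in or near the ward, and gives loss to follow-up as the reason. The protocol therefore selects one group on a factor that it ties to the outcome itself, and states no such rule for the other group.

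Time in care is also uncontrolled. The study group mixes newly diagnosed people with people already in care, in unknown proportions. The comparators are existing patients, perhaps with some new ones. With no month 1 defined for either group, one person's 18 months may cover the first months after diagnosis and another's may start after years of settled care.

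What is at stake is the wording of the result. A coefficient that reflects enrollment rules and treatment history could be reported as the effect of dyadic care.

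**Working it through.** **The plan's own figures.** No effect size or power is given for this comparison. The one power statement (Precision of Estimates and Statistical Power, AIM 2) starts from 50 people x 3 occasions = 150 and ICC .50. It reproduces: 150 / (1 + 2 x 0.50) = 75. That calculation is for a time-varying level-1 predictor, not for the level-2 group indicator, so it neither supports nor refutes the point.

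**What is specified for each group.**

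| Feature | Study positives | Comparators |
|---|---|---|
| Cohabiting, no plans to move, disclosure | required | not stated |
| Adequate tracing data | required | not stated |
| Lives in or near the ward | required of clinic recruits; self-testing couples are sampled within the ward | not stated |
| Time in care | new and established | existing patients, no limit stated |
| Month 1 | not defined | not defined |
| Adjustment covariates | none committed to | none committed to |

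**Illustration.** The documents give no retention rates or group shares, so every input below is assumed. The true dyadic effect is set to zero.
- Monthly retention is 85% in settled local patients and 65% in comparators living outside the listed towns.
- Share of established comparators living outside: w = 0.2 or 0.4.
- Retention of new patients, the same in both groups: r = 0.60 or 0.75.
- Share new among study positives: ns = 0.50 or 0.25. Share new among comparators: nc = 0.20 or 0.25.

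Study: p = 0.85(1 - ns) + r x ns.
Comparator: p = (1 - nc)[0.85(1 - w) + 0.65w] + r x nc.
Crude OR = ratio of the two odds.

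Low end (ns 0.50, nc 0.20, r 0.60, w 0.2): study p = 0.425 + 0.300 = 0.725; comparator p = 0.8 x 0.81 + 0.12 = 0.768; OR = (0.725/0.275) / (0.768/0.232) = 2.636/3.310 = 0.80.

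High end (ns 0.25, nc 0.25, r 0.75, w 0.4): study p = 0.6375 + 0.1875 = 0.825; comparator p = 0.75 x 0.77 + 0.1875 = 0.765; OR = 4.714/3.255 = 1.45.

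| New: study / clinic | r | OR, w = 0.2 | OR, w = 0.4 |
|---|---|---|---|
| 50% / 20% | 0.60 | 0.80 | 0.95 |
| 50% / 20% | 0.75 | 1.01 | 1.22 |
| 25% / 20% | 0.60 | 1.12 | 1.33 |
| 25% / 20% | 0.75 | 1.19 | 1.44 |
| 25% / 25% | 0.60 | 1.19 | 1.39 |
| 25% / 25% | 0.75 | 1.22 | 1.45 |

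The first row falls below 1 because the study group holds more new patients, which outweighs its residence advantage. The last two rows have equal time in care, and residence alone leaves 1.19-1.45. If residence is equalised as well (w = 0, ns = nc), the OR is 1.00. That follows by construction, since residence is the only selection factor in this model.

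**Refill denominator.** AIM 2 introduces the refill indicator for people on ARV, then assigns 18 monthly values to every positive individual. The two sentences need to agree.

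**The case against.** The best defence is that the plan claims little and leaves room. It says "This is an exploratory study primarily investigating operational research issues", concedes limited precision, provides for model building and intends to compare client characteristics. With about 50 positives followed, random error may exceed the bias illustrated here.

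Much of this stands. It limits the weight of the point, and it means that covariates are absent only in the sense that none is committed to. It does not remove the point. The clinic data stand in for a control arm on exactly these outcomes, and the aim is worded as an effect. Comparing characteristics shows imbalance without removing it, choosing terms after viewing outcome plots is not pre-specification, and bias does not shrink as the comparator set grows. It is also fair that residence is not among the listed clinic-database fields, and that disclosure is partly intrinsic to enrolling as a couple rather than purely a confounder.

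Four stronger readings are tempting and are not supported:
- *The comparison is bound to favour couple care.* Selection on stability may do so, but a larger share of newly diagnosed people may do the reverse.
- *The distortion could be much larger.* That needs something like half of the comparators to be new, against a group described as an existing patient population.
- *The pandemic corrupts the comparison.* The plan does say "CTC2 card data extraction will pause beginning 1st May 2020", but Utilization and Clinical Data Collection has visit data abstracted later. A pause in extraction does not mean lost months, and nothing says it affects one group more.
- *Untreated months will be scored as missed refills.* The earlier AIM 2 sentence points to people on ARV; the later wording is loose, not a clear instruction to do this.

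**Conclusion.** The concern holds and should be fixed before analysis. As written, the retention, refill and 18-month CD4 contrasts cannot separate a dyadic effect from enrollment rules and time in care. The sign of the resulting bias cannot be read from the documents.

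On the assumed rates, with no true effect and 20-25% new patients among comparators, the crude OR lies between about 0.80 and 1.45. This shows what is plausible and predicts nothing: shares, retention rates and the size of the residence difference are all assumed. The range covers retention only, since neither refill nor CD4 was modelled. The study's descriptive results on uptake, safety and acceptability are untouched.

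**What to change.** 1. **Common time origin.** For retention and refill, start the clock for study positives at the later of study enrollment and first CTC care visit. For comparators, start at a clinic-database month in which the patient is in care, matched on calendar period and time since enrollment in CTC care. Under Enrollment in HIV Care as a Couple, consent comes before referral to the CTC. Starting at enrollment would therefore count pre-linkage months against study positives only. Report linkage before month 1 separately.
2. **Refill denominator.** Score refill only for months at or after ART start in both groups, count later lapses, and make the two AIM 2 sentences agree that the measure concerns people on ARV.
3. **Covariates.** Pre-specify age, sex, baseline CD4 and time since enrollment in CTC care at month 1 for retention and refill. Add baseline CD4 to the 18-month CD4 model.
4. **Comparator restriction.** Limit comparators to age 18 or above, and apply the residence and partnership criteria only where the clinic database records them.
5. **Wording.** Report an adjusted association, and state that residence, relocation plans and disclosure may remain uncontrolled.

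The cost is SAP text and modest programming. The clinic database is described as holding patient characteristics, enrollment, pharmacy and CD4 data, and the Measures section has prescription and pick-up dates for both groups. The downsides are a smaller comparator set, some missing baseline CD4 and only partial control of confounding.

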Data Structure: There are two key unique features of the primary data for this proposal. First, because couples are enrolled in the study, there is inherent nesting of two individuals within each couple. Second, the measurement design leads to repeated measurements outcomes for some of the aims. Given the aims of the study, many of the outcomes will be evaluated using descriptive statistics. However, issues such as nesting and repeated measurements will be carefully considered. For example, for the first aim, uptake will be reported by each individual within the couple, and the descriptive statistics will be reported both at the individual level within the couple and at the aggregate couple level. For the outcomes that will be evaluated using inferential statistical analyses, the nested data structures (e.g., repeated measurements within couples) will be addressed using mixed-effects regression models (MRMs; e.g.).⁸¹ These highly flexible models accommodate variability in the number/spacing of outcome measurements, and they readily accommodate linear and non-linear outcome distributions (e.g., dichotomous, count). **Outcome Distributions & Individual Trajectories:** Prior to analysis, each outcome will be carefully inspected to determine the most appropriate distribution for modeling. Likewise, for outcomes with repeated measurements, the trajectory for each participant on each outcome will be plotted using “spaghetti plots”.⁸² These plots will illustrate the level of and variability in each outcome, along with patterns of change over time. **Model Building & Estimation:** Singer and Willett’s (2003)⁸³ model building approach will be used to specify fixed and random effects. The MRMs will be performed using MLwiN software.⁸⁴ Due to the relatively modest sample size for some of the analyses, the models will also be performed using Bayesian MCMC-based estimation⁸⁵ in MLwiN. This simulation-based approach utilizes a large number of iterations – each informing the next – to produce an empirically-based sampling distribution for each parameter. For example, rather than a single point estimate of the parameter of interest, the MCMC-based provides the magnitude, precision, and variability of the parameter estimates. **Attrition & Missing Data:** Individuals or couples who drop out of clinic care will be retained, when possible, in ongoing research measurement according to Intention-to-treat principles.⁸⁶ Some research data will inevitably be missing, and the methods recommended by Schafer and Graham⁸⁷ will be used to evaluate missing data assumptions and guide the subsequent analyses. Given few missing data and evidence supporting a MAR mechanism, the procedures detailed above will be utilized with all available data. Given non-trivial missing data and evidence supporting MAR, multiple imputation for longitudinal data will be used to provide complete data.⁸⁸ Finally, given non-trivial missing data and evidence suggesting NMAR, pattern mixture models will be used to control the missing data.⁸²

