first outcome, self-reported ARV adherence, the three repeated measurements will be nested within the positive partners. The unconditional model will estimate the rate of, and variability in, ARV adherence across participants. Based on inspection of "spaghetti plots," subsequent level-1 growth models will be specified to test for change in the rate of ARV adherence over time. For the second outcome, each positive individual from the study and from the CTC will have 18 monthly measurements of ARV refill status (i.e., 0 = Not Refilled, 1 = Refilled). This will be modeled as described above, with the level-2 dichotomous indicator testing for a difference in the average log-odds of adherence for those enrolled as a couple and those enrolled in routine clinic care. Given the large number of measurements per individual, alternative specifications are possible, and this will be guided by inspection of the spaghetti plots. For the third outcome, CD4 counts at 18 months will be compared using a single-level regression model to test for differences between those enrolled as a couple and those enrolled in routine services. For the fourth outcome, sexual frequency, condom use, and sex in the context of ARV or PrEP will be estimated. Using a mixed-effects model, predictor variables related to risk will be added to the model. These variables will also be considered for entry as time-varying covariates (i.e., entry at level-1) or as aggregative, couple-specific predictors.

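### Aim 2 tests 18 monthly refill values per person as adherence without saying how months after death, transfer or leaving care are handled, so a retention difference could appear again as an adherence difference

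*Combined protocol and SAP*

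**What the plan says.** All of this is in the combined protocol and SAP, section D.

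- **Hypothesis (AIM 2).** Couples who enter care together will "have higher rates of adherence and retention than individually enrolled clients". Two benefits are named.
- **Retention model (AIM 2).** A person-level indicator "will test for differences in the log-odds of treatment retention between those enrolled in care as a couple" and those in routine services. Retention is not defined operationally.
- **Refill model (AIM 2, second outcome).** "each positive individual from the study and from the CTC will have 18 monthly measurements of ARV refill status", with only two codes, "0 = Not Refilled, 1 = Refilled". The same kind of indicator is used, "testing for a difference in the average log-odds of adherence for those enrolled as a couple and those enrolled in routine clinic care".
- **What a refill requires (AIM 2).** "individuals on ARV are expected to return to the clinic each month to have the prescription refilled". Attendance and refill are therefore closely tied.
- **People who leave (Analysis Plan, Attrition & Missing Data).** "Individuals or couples who drop out of clinic care will be retained, when possible, in ongoing research measurement according to Intention-to-treat principles". For gaps in the data: "Given non-trivial missing data and evidence supporting MAR, multiple imputation for longitudinal data will be used to provide complete data". If few data are missing, all available data are used; if the data look not missing at random, pattern mixture models are used. None of these rules mentions refill months after exit.
- **Other indicators.** AIM 2 describes self-reported adherence and the 18-month viral load for study participants. The section on clinical data from the Care and Treatment Center (CTC) also mentions comparing viral suppression with other clinic patients, and AIM 2 compares 18-month CD4 counts between the groups. Refill is the only medication-adherence indicator with a between-group model specified for both groups.

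**The concern.** Every person can have 18 binary values only if months after exit are given a value. On that literal reading, someone who leaves, transfers or dies after month 9 contributes 18 − 9 = 9 values of Not Refilled. A group that keeps more patients would then show better refill even if those in care collect their drugs equally regularly in both groups. Deaths and transfers would count as non-adherence.

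The other routes do not settle the matter. Multiple imputation would supply refill values for people who have died or whose refills are now collected elsewhere. Using all available data would drop the later months, but the plan gives no date at which a person's series ends.

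A retention gap is foreseeable from the design alone. Study participants must have no plans to move. Couples recruited at the CTC must live in or near the ward, a rule the protocol explains as limiting loss to follow-up. Positive partners who choose another CTC are excluded, and participants receive study phones. No such conditions are stated for the comparison patients. A gap arising from selection could be reported as two favourable findings.

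**Working it through.** **Is there a figure to reproduce?** No. The power section treats a level-1 predictor within couples, not this between-group contrast. The only loss figure in the plan is an allowance of up to 20% for the enrolled couples; nothing is given for clinic patients.

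**Assumptions (not in the documents).** Refill while in care is 95% of months in both groups, so the true in-care odds ratio is 1. Eighteen-month retention is 90% in the couple group and 85%, 80% or 70% in routine care. Months after exit are scored 0.

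**Step 1: share of the 18 months in care, loss spread evenly.** Share = r + (1 − r)/2.
- r = 0.90: 0.950
- r = 0.85: 0.925
- r = 0.80: 0.900
- r = 0.70: 0.850

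**Step 2: expected all-month refill = 0.95 × share.** This gives 0.9025, 0.8788, 0.8550 and 0.8075.

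**Step 3: odds ratio against the 90% group, whose odds are 0.9025/0.0975 = 9.26.**
- vs 85%: 0.8788/0.1212 = 7.25; OR = 9.26/7.25 = 1.28
- vs 80%: 0.8550/0.1450 = 5.90; OR = 9.26/5.90 = 1.57
- vs 70%: 0.8075/0.1925 = 4.19; OR = 9.26/4.19 = 2.21

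With a constant monthly exit rate instead of even loss, the shares are 0.946, 0.919, 0.891 and 0.833, and the odds ratios are 1.30, 1.62 and 2.35. The in-care rate matters as well: at 90% vs 80% retention with constant exit, the odds ratio is 1.26, 1.42 and 1.62 for in-care refill of 80%, 90% and 95%.

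**Step 4: how often would this be significant?** Simulated trials with no true in-care difference, two-sided 5% level:

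| Assumptions | Retention | All 18 months, zeros after exit | In-care months only |
|---|---|---|---|
| 95% in-care refill, 60 vs 300 patients | 90% vs 85% | 22% | 4–6% |
| same | 90% vs 80% | 47% | 4–6% |
| same | 90% vs 70% | 91% | 4–6% |
| 90% mean in-care refill varying between people, 60 vs 200 or 500 | 90% vs 90% | 6% | 5–6% |
| same | 90% vs 80% | 38–47% | 6% |
| same | 90% vs 70% | 84–90% | 5–6% |

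The equal-retention row shows that the excess comes from retention. In the second set, each person's all-month refill share correlates 0.83 to 0.93 with the share of months in care. At 90% vs 80% retention, the refill and retention tests are both significant in 28–36% of trials. The all-month test in that set was a person-level Welch test, not the planned mixed model, so the percentages are indicative.

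**The case against.** The strongest reply is that the plan never says months after exit are zeros. The 18 values may only describe the intended schedule. The Analysis Plan says the mixed models tolerate varying numbers of measurements, it has a missing-data section, and AIM 2 introduces the refill indicator for people on ARV. This stands. A reader might infer that the plan definitely scores those months as Not Refilled; the documents do not support that. They support only that the rule is missing and that the literal reading leads there.

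A reader might also infer that refill merely restates retention, so that one effect is counted twice across the whole adherence claim. That goes too far. Refill mixes staying in care with collecting drugs while in care, and self-report, viral load and CD4 are also in the plan. The overlap concerns the refill comparison.

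Two further points have weight. Refill coverage over a fixed window is a legitimate measure of adherence including persistence, provided it is named as such. And an in-care analysis conditions on staying. If each series were cut at the last attended visit, the final run of missed refills would vanish: in a simulated check, in-care refill came out at about 95% in both groups even when one group stopped collecting ARV three times as fast. The cut-off must therefore be chosen differently.

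The study calls itself exploratory, which limits the severity. It does not remove the problem, because the plan still states a between-group adherence hypothesis.

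**Conclusion.** The concern holds as an unspecified rule with material consequences. The plan promises 18 binary refill values for everyone, tests them as adherence with the same contrast as retention, and is silent on months after death, transfer or leaving care. If those months are zeros, equal in-care refill of 95% would give a spurious odds ratio of about 1.3, 1.6 or 2.2 at retention of 90% vs 85%, 80% or 70%. If they are imputed, refills would be created for people who have died or transferred. If they are omitted at a properly defined exit, the artefact largely disappears.

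The sizes rest on assumed retention and refill rates and on zeros after exit, none of which the documents state. With equal retention there is no distortion. The point should be settled in the SAP before the comparison is run, particularly as AIM 2 lets the model form follow inspection of the plotted data.

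**What to change.** Add the following to the AIM 2 analysis text:

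1. End each person's refill series at death or recorded transfer. Neither score later months as 0 nor impute them.
2. Define retention, and a loss-to-follow-up date, by one prespecified rule applied identically to study and routine patients. Do not use the last attended visit, so that missed refills before the loss date still count.
3. Report refill among months in care beside the retention result, and state that it is conditional on remaining in care.
4. If the all-month refill measure is kept, label it the composite of retained and refilled, and do not present it as adherence evidence separate from retention.

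**Cost.** SAP wording and a little more analysis. Visit dates, prescription pick-up dates, and medication change or stop events with reasons are already to be collected for both groups (Measures, Clinical item). The drawback is that the in-care result cannot be read alone; it must be interpreted together with retention.
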